6.3.1.1 DF/HCC Expedited Reporting Guidelines

Investigative sites within DF/HCC and DF/PCC will report SAEs directly to the DFCI Office for Human Research Studies (OHSR) per the DFCI IRB reporting policy.

Other investigative sites will report SAEs to their respective IRB according to the local IRB's policies and procedures in reporting adverse events. A copy of the submitted institutional SAE form should be forwarded to the Overall PI within the timeframes detailed in the table below.

Attribution	DF/HCC Reportable AEs			
	Gr. 2 & 3 AE Expected	Gr. 2 & 3 AE Unexpected	Gr. 4 AE Unexpected	Gr. 5 AE Expected or Unexpected
Unrelated Unlikely	Not required	Not required	5 calendar days	1 working day
Possible Probable Definite	Not required	5 calendar days	5 calendar days	1 working day

* For participants enrolled and actively participating in the study **or** for AEs occurring within 90 days of the last intervention (or the initiation of new anti-cancer therapy, whichever is earlier), the AE should be reported within 1 working day of learning of the event.

The Overall PI will submit SAE reports from outside institutions to the DFCI OHRs according to DFCI IRB policies and procedures in reporting adverse events.

6.3.1.2 Expedited Reporting to the Food and Drug Administration (FDA)

The Overall PI, as study sponsor, will be responsible for all communications with the FDA. The Overall PI will report to the FDA, regardless of the site of occurrence, any serious adverse event that meets the FDA's criteria for expedited reporting following the reporting requirements and timelines set by the FDA.

6.3.1.3 Expedited Reporting to Hospital Risk Management

Participating investigators will report to their local Risk Management office any participant safety reports or sentinel events that require reporting according to institutional policy.

6.3.1.4 Routine Adverse Event Reporting

All Adverse Events **must** be reported in routine study data submissions to the Overall PI on the toxicity case report forms. **AEs reported through expedited processes (e.g., reported to the IRB, FDA, etc.) must also be reported in routine study data submissions.**

6.3.1.5 Protocol-Specific Expedited Adverse Event Reporting Exclusions

For this protocol only, the AEs/grades listed below do not require expedited reporting to the Overall PI, the DFCI IRB or Merck. However, they still must be reported through the routine reporting mechanism (i.e. case report form).

- Lymphopenia (grades 2-4)
- A visit to the emergency room or other hospital department < 24 hours, that does not result in admission (unless considered an important medical or life-threatening event)
- Emergency outpatient treatment for an event not fulfilling the serious criteria outlined above in section 6.3.1 and not resulting in inpatient admission
- Elective surgery, planned prior to signing consent
- Routine health assessment requiring admission for baseline/trending of health status (eg, routine colonoscopy)

- Hospitalization for routine treatment or monitoring of the studied indication, not associated with any deterioration in condition, or for elective procedures
- Hospitalization for seizure, if felt related to patient's underlying disease
- Hospitalization for elective or pre-planned treatment for a pre-existing condition that did not worsen
- Hospitalization for respite care not associated with an adverse event attributed to the study drug
- Hospitalization for surgical intervention in order to delineate pseudoprogression due to inflammation associated with PD-1 blockade from true tumor progression as mentioned in section 10.5.

6.3.2 Events of Clinical Interest

Selected non-serious and serious adverse events are also known as Events of Clinical Interest (ECI) and must be reported within 1 working day to the DFCI Coordinating Center and Overall PI and within 2 working days to Merck Global Safety. (Attn: Worldwide Product Safety; [contact])

Events of clinical interest for this trial include:

1. an overdose of Merck product, as defined in Section 6.1 - Definition of an Overdose for This Protocol and Reporting of Overdose to the Sponsor, that is not associated with clinical symptoms or abnormal laboratory results.
2. an elevated AST or ALT lab value that is greater than or equal to 3X the upper limit of normal and an elevated total bilirubin lab value that is greater than or equal to 2X the upper limit of normal and, at the same time, an alkaline phosphatase lab value that is more than 2X the upper limit of normal, as determined by way of protocol-specified laboratory testing or unscheduled laboratory testing.*

***Note:** These criteria are based upon available regulatory guidance documents. The purpose of the criteria is to specify a threshold of abnormal hepatic tests that may require an additional evaluation for an underlying etiology.

ECIs that occur in any subject from the date of first dose through 90 days following cessation of treatment, or the initiation of a new anticancer therapy, whichever is earlier, whether or not related to the Merck's product, must be reported within 1 working day to the DFCI Coordinating Center and Overall PI and to Merck Global Safety within 2 working days.

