5.2 Dose Selection/Modification

Dose Selection

The rationale for selection of doses to be used in this trial is provided in Section 2.3.2 – Background and Rationale.

Details on preparation and administration of pembrolizumab (MK-3475) are provided in the Pharmacy Manual.

Dose Modification

No dose reductions (in dose or frequency) are permitted. Only dose holds are permitted per protocol. Treatment may be held for up to 12 weeks (84 days) from last dose.

Adverse events (both non-serious and serious) associated with pembrolizumab exposure may represent an immunologic etiology. These adverse events may occur shortly after the first dose or several months after the last dose of treatment. Pembrolizumab must be withheld for drug-related toxicities (considered at least possibly related to study treatment) and severe or life-threatening AEs as per Table 3 below. If a participant experiences a toxicity unlikely or unrelated to treatment

with pembrolizumab, but may still warrant a hold or reduction of study drug for safety, discussion and writing approval by the Overall Principal Investigator and Study Sponsor, [name], is recommended but not required.

See Section 5.7 for supportive care guidelines, including use of corticosteroids.

Table 3 Dose Modification Guidelines for Drug-Related Adverse Events

Toxicity	Hold Treatment For Grade	Timing for Restarting Treatment	Treatment Discontinuation
Diarrhea/Colitis	2-3	Toxicity resolves to Grade 0-1.	Toxicity does not resolve within 12 weeks of last dose or inability to reduce corticosteroid to 10 mg or less of prednisone or equivalent per day within 12 weeks.
	4	Permanently discontinue	Permanently discontinue
AST, ALT, or Increased Bilirubin	2	Toxicity resolves to Grade 0-1	Toxicity does not resolve within 12 weeks of last dose.
	3-4	Permanently discontinue (see exception below) ¹	Permanently discontinue
Type 1 diabetes mellitus (if new onset) or Hyperglycemia	T1DM or 3-4	Hold pembrolizumab for new onset Type 1 diabetes mellitus or Grade 3-4 hyperglycemia associated with evidence of beta cell failure.	Resume pembrolizumab when patients are clinically and metabolically stable within 12 weeks of last dose.
Hypophysitis	2-4	Toxicity resolves to Grade 0-1. Therapy with pembrolizumab can be continued while endocrine replacement therapy is instituted	Toxicity does not resolve within 12 weeks of last dose or inability to reduce corticosteroid to 10 mg or less of prednisone or equivalent per day within 12 weeks.

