- **INVESTIGATIONS**: activated partial thromboplastin time prolonged; alanine aminotransferase increased; alkaline phosphatase increased; aspartate aminotransferase increased; blood bilirubin increased; creatinine increased; GGT increased; INR increased; neutrophil count decreased; platelet count decreased; weight loss
- **METABOLISM AND NUTRITION DISORDERS**: anorexia; hypoalbuminemia; hyponatremia
- **MUSCULOSKELETAL AND CONNECTIVE TISSUE DISORDERS**: myalgia; arthralgia; arthritis; myositis; Rhabdomyolysis
 - Musculoskeletal and connective tissue disorders – Other, specify: myopathy; rejection of solid organ or tissue transplants (corneal, kidney, or liver)
- **NERVOUS SYSTEM DISORDERS** *: dizziness; dysgeusia; edema cerebral; headache; peripheral motor neuropathy; peripheral sensory neuropathy; seizures;

- Nervous system disorders – other, specify: Guillain-Barre syndrome; myasthenia gravis (MG)
- **PSYCHIATRIC DISORDERS:** confusion
- **RENAL AND URINARY DISORDERS ***: hematuria;
 - Renal and urinary disorders – other, specify: nephritis
- **REPRODUCTIVE SYSTEM AND BREAST DISORDERS ***
- **RESPIRATORY, THORACIC AND MEDIASTINAL DISORDERS ***: cough; dyspnea; pneumonitis
- **SKIN AND SUBCUTANEOUS TISSUE DISORDERS:** exfoliative dermatitis
 - All CTCAE rashes are considered expected: bullous dermatitis; erythema multiforme; erythroderma; palmar-plantar erythrodysesthesia syndrome; pruritus; rash acneiform; rash maculo-papular; skin hyperpigmentation; skin hypopigmentation; skin induration; skin ulceration; Stevens-Johnson syndrome; toxic epidermal necrolysis (TEN) ;
 - Skin and subcutaneous tissue disorders – other, specify: pemphigus; vitiligo
- **VASCULAR:** vasculitis

* In addition, the following adverse event is considered expected within all applicable SOCs:

- bleeding/hemorrhage

Table 5 Evaluating Adverse Events

Appropriately delegated study team members will evaluate all adverse events as to:

V5.0 CTCAE Grading	Grade 1	Mild; asymptomatic or mild symptoms; clinical or diagnostic observations only; intervention not indicated.
	Grade 2	Moderate; minimal, local or noninvasive intervention indicated; limiting age-appropriate instrumental ADL.
	Grade 3	Severe or medically significant but not immediately life-threatening; hospitalization or prolongation or hospitalization indicated; disabling; limiting self-care ADL.
	Grade 4	Life threatening consequences; urgent intervention indicated.
	Grade 5	Death related to AE

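### The hepatic event of clinical interest also requires ALP above 2X ULN, so non-serious transaminase-plus-bilirubin elevation with lower ALP has no automatic expedited report and no required collection on days 31-90

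*Combined protocol and SAP*

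**What the plan says.** Section 6.3.2 names two ECIs. Item 1 is an overdose without symptoms or abnormal laboratory results. Item 2 is hepatic and sets three limits, all of which must be met. The transaminase limit is "an elevated AST or ALT lab value that is greater than or equal to 3X the upper limit of normal". Total bilirubin must also reach 2X ULN or more. The third limit is "at the same time, an alkaline phosphatase lab value that is more than 2X the upper limit of normal". The note below it attributes the criteria to regulatory guidance and gives their purpose, which is to "specify a threshold of abnormal hepatic tests that may require an additional evaluation for an underlying etiology".

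ECI status has three consequences.
- **Reporting.** An ECI arising from first dose to 90 days after treatment ends (or to new anticancer therapy, if earlier), whether or not related, "must be reported within 1 working day to the DFCI Coordinating Center and Overall PI and to Merck Global Safety within 2 working days". Section 6.3.1 handles non-serious ECIs like serious adverse events (SAEs).
- **Collection.** Under Section 6 and footnote p of the Study Calendar, ordinary adverse events are recorded to about 30 days after the last dose. The window to 90 days covers only SAEs and ECIs.
- **Analysis.** Section 12.2.4.2 includes ECIs in the safety assessment. Section 12.2.6.2 summarises them separately by grade, with counts, percentages and 95% CIs.

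The hepatic row of Table 3 in Section 5.2 is labelled "AST, ALT, or Increased Bilirubin" and has no ALP term. Section 6.4 lists "alanine aminotransferase increased; alkaline phosphatase increased; aspartate aminotransferase increased; blood bilirubin increased" as expected, and hepatitis as well.

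**The concern.** The note describes a screen for abnormal liver tests whose cause needs working up. A combined rise in transaminases and bilirubin is such a finding whatever the ALP, yet the third limit removes every such case with ALP at or below 2X ULN. Table 3 treats the same transaminase and bilirubin abnormalities as drug toxicity without looking at ALP. An event serious enough to stop study drug under Table 3 can therefore fall outside the only hepatic ECI.

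Safety is a primary objective in both stages (Section 1.2.3), and the ECI route is the one that does not depend on a judgement of seriousness or relatedness. If it cannot fire for one pattern of liver injury, early notice of non-serious cases depends on discretion, and the hepatic line of the ECI table could read zero although such cases occurred.

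**Working it through.** The plan gives no figure to reproduce here. The check is to apply the definition as written and then follow an excluded case through the other reporting routes.

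**Step 1: the rule.** With all values in multiples of ULN, a hepatic ECI is: (AST or ALT ≥ 3) and (bilirubin ≥ 2) and (ALP > 2). The thresholds are those in 6.3.2. The profiles below are illustrative assumptions. The last two columns are for comparison.

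| ALT | Bilirubin | ALP | As written | ALP limit deleted | ALP limit reversed (< 2) |
|---|---|---|---|---|---|
| 20 | 5 | 1.0 | no | yes | yes |
| 10 | 3 | 1.5 | no | yes | yes |
| 20 | 5 | 2.0 | no | yes | no |
| 3 | 2 | 2.1 | yes | yes | no |
| 20 | 5 | 2.1 | yes | yes | no |
| 2.9 | 5 | 5.0 | no | no | no |

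A grid of five ALT values (3 to 40), four bilirubin values (2 to 10) and four ALP values (0.5 to 2.0) gives 5 × 4 × 4 = 80 profiles. All meet the first two limits; 0 of 80 are ECIs as written. The last row shows that cholestasis without the transaminase rise is not flagged either, so the cases now captured are mixed patterns.

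**Step 2: effect of deletion.** Any case meeting all three limits also meets the first two. Deleting the ALP limit can only add cases. Reversing it adds some and drops others (rows 4 and 5).

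**Step 3: other routes for an excluded case (ALT 20X, bilirubin 5X, ALP 1X).**
- *Onset on treatment or within 30 days.* It goes on the adverse event form (6.3.1.4), due within 14 days (11.2), and Table 3 applies.
- *Serious or life-threatening.* It is expedited as an SAE (6.3.1). Appendix B Section 3.10 also requires immediate reporting of life-threatening toxicity.
- *Non-serious.* The liver terms are expected, so the table in 6.3.1.1 asks for no expedited report at grade 2-3. Its only grade 4 column is for unexpected events. No automatic trigger remains.
- *Non-serious, first arising on days 31-90.* Neither an SAE nor an ECI, it need not be collected.

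**Step 4: size in the analysis.** The plan gives no incidence for this pattern, so no expected count can be derived. For scale, with about 30 + 20 = 50 evaluable patients, one case is 1/50 = 2.0 percentage points. If all 35 patients enrolled at the interim and 25 in Stage 2 were treated, it is 1/60 = 1.7 points.

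**The case against.** The strongest reply is that little depends on ECI status. All CTCAE-graded events are safety endpoints under 12.2.4.2, and laboratory assessments are too. Table 3 acts on AST, ALT and bilirubin regardless of ALP. Life-threatening and serious events are expedited by other clauses, and Section 5.9 requires immediate notice to the Overall PI of unusual or life-threatening complications. Patients removed for unacceptable events are followed to resolution or stabilisation (5.10). Participating sites report holds and significant events on calls held at least monthly (Appendix B Section 5.1). Table 3 governs dosing, so its lack of an ALP term does not strictly contradict a reporting rule.

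Most of this stands, and it defeats one reading that a reader might infer: that severe liver injury with low ALP goes unnoticed in the trial. It does not close the gap for non-serious events, because each route either depends on seriousness, lacks the one-working-day clock, or ends at day 30 for new onsets.

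Section 12.2.6.2 might also rescue the case, since it has adverse events of unknown cause assessed as possible immune-related ECIs. But it is an analysis provision without a reporting deadline, and it takes its definitions from a Section 7.3.2 that this document does not contain.

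A second tempting reading is that the inequality was simply reversed and should say less than 2X. The documents do not show this. The guidance named in the note is not reproduced, so the intended direction cannot be confirmed, and reversal would drop cases now captured.

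**Conclusion.** The definition is wrong as written and should be fixed. It excludes every combined transaminase and bilirubin elevation with ALP at or below 2X ULN, which fits poorly with the note's stated purpose. This follows from the wording alone and needs no outside source.

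The practical loss is narrower: for non-serious cases there is no automatic expedited report, no entry in the hepatic ECI summary, and no required collection if onset is on days 31-90. It does not affect the primary biomarker tests or on-treatment adverse event recording.

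Two further inferences should be avoided. The total exclusion is a property of the rule and says nothing about how often the pattern occurs. Nor does the rule select the wrong patients: anyone meeting all three limits also has a marked liver abnormality. The conclusion assumes that 6.3.2 is the operative ECI list, as no other ECI list appears in the document.

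**What to change.** 1. Check the ALP limit in 6.3.2 item 2 against the regulatory guidance that the note cites, and name that source in the note.
2. Unless the source supports the limit, delete it, so that AST or ALT at least 3X ULN with total bilirubin at least 2X ULN is enough.
3. Re-screen existing chemistry results against the corrected definition. AST, ALT, bilirubin and ALP are all in the serum chemistry panel (Study Calendar, footnote t). Add any case found to the ECI summary.
4. In 12.2.6.2, replace the references to Section 7.3.2 with 6.3.2 for the ECI list. Section 6.3.2 does not define immune-related adverse events, so that definition must be supplied or located separately.

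The cost is a short amendment and one listing from data already held. The downside is possibly a few more ECI reports.

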6.4 Evaluating Adverse Events

An investigator will evaluate all adverse events according to the NCI Common Terminology for Adverse Events (CTCAE), version 5.0. Any adverse event which changes CTCAE grade over the course of a given episode will have each change of grade recorded on the adverse event case report forms/worksheets.

All adverse events regardless of CTCAE grade must also be evaluated for seriousness as defined in Section 6.3.1 and Table 5. In addition, attribution of AEs must be classified based on the following definitions:

- Definite – The AE is *clearly related* to the study treatment.
- Probable – The AE is *likely related* to the study treatment.
- Possible – The AE *may be related* to the study treatment.
- Unlikely – The AE is *doubtfully related* to the study treatment.
- Unrelated – The AE is *clearly NOT related* to the study treatment.

In order for an event to be considered expected (known correlation to study drug) for the purposes of adverse event reporting, the event must be included in the section below. This list of adverse events categorized by CTCAE v. 5.0 is derived from the current pembrolizumab Investigator Drug Brochure. If a treating investigator would like to consider an adverse event expected that is not listed below, discussion with the DFCI Coordinating Center, is required.

- **BLOOD AND LYMPHATIC SYSTEM DISORDERS** *: anemia
- **CARDIAC DISORDERS**: heart failure; myocarditis
- **ENDOCRINE DISORDERS**: adrenal insufficiency; hyperthyroidism; hypothyroidism;
 - Endocrine disorders – other, specify: hypophysitis; thyroiditis; type 1 diabetes mellitus
- **EYE DISORDERS** *: uveitis;
 - Eye disorders – other, specify: iritis
- **GASTROINTESTINAL DISORDERS** *: abdominal pain; colitis; constipation; diarrhea; nausea; pancreatitis; vomiting
- **GENERAL DISORDERS AND ADMINISTRATION SITE CONDITIONS**: edema limbs; fatigue; fever; infusion related reaction
- **HEPATOBILIARY DISORDERS** *:
 - Hepatobiliary disorders – other, specify: hepatitis, sclerosing cholangitis
- **IMMUNE SYSTEM DISORDERS**: allergic reaction
- **INFECTIONS AND INFESTATIONS**: skin infection; urinary tract infection; upper respiratory infection;
 - Infections and infestations – other, specify: pneumonia
- **INJURY, POISONING AND PROCEDURAL COMPLICATIONS** *
- **INVESTIGATIONS**: activated partial thromboplastin time prolonged; alanine aminotransferase increased; alkaline phosphatase increased; aspartate aminotransferase increased; blood bilirubin increased; creatinine increased; GGT increased; INR increased; neutrophil count decreased; platelet count decreased; weight loss
- **METABOLISM AND NUTRITION DISORDERS**: anorexia; hypoalbuminemia; hyponatremia
- **MUSCULOSKELETAL AND CONNECTIVE TISSUE DISORDERS**: myalgia; arthralgia; arthritis; myositis; Rhabdomyolysis
 - Musculoskeletal and connective tissue disorders – Other, specify: myopathy; rejection of solid organ or tissue transplants (corneal, kidney, or liver)
- **NERVOUS SYSTEM DISORDERS** *: dizziness; dysgeusia; edema cerebral; headache; peripheral motor neuropathy; peripheral sensory neuropathy; seizures;

- Nervous system disorders – other, specify: Guillain-Barre syndrome; myasthenia gravis (MG)
- **PSYCHIATRIC DISORDERS:** confusion
- **RENAL AND URINARY DISORDERS ***: hematuria;
 - Renal and urinary disorders – other, specify: nephritis
- **REPRODUCTIVE SYSTEM AND BREAST DISORDERS ***
- **RESPIRATORY, THORACIC AND MEDIASTINAL DISORDERS ***: cough; dyspnea; pneumonitis
- **SKIN AND SUBCUTANEOUS TISSUE DISORDERS:** exfoliative dermatitis
 - All CTCAE rashes are considered expected: bullous dermatitis; erythema multiforme; erythroderma; palmar-plantar erythrodysesthesia syndrome; pruritus; rash acneiform; rash maculo-papular; skin hyperpigmentation; skin hypopigmentation; skin induration; skin ulceration; Stevens-Johnson syndrome; toxic epidermal necrolysis (TEN) ;
 - Skin and subcutaneous tissue disorders – other, specify: pemphigus; vitiligo
- **VASCULAR:** vasculitis

* In addition, the following adverse event is considered expected within all applicable SOCs:

- bleeding/hemorrhage

Table 5 Evaluating Adverse Events

Appropriately delegated study team members will evaluate all adverse events as to:

V5.0 CTCAE Grading	Grade 1	Mild; asymptomatic or mild symptoms; clinical or diagnostic observations only; intervention not indicated.
	Grade 2	Moderate; minimal, local or noninvasive intervention indicated; limiting age-appropriate instrumental ADL.
	Grade 3	Severe or medically significant but not immediately life-threatening; hospitalization or prolongation or hospitalization indicated; disabling; limiting self-care ADL.
	Grade 4	Life threatening consequences; urgent intervention indicated.
	Grade 5	Death related to AE
Seriousness	A serious adverse event is any adverse event occurring at any dose or during any use of Merck product that:	
	† Results in death; or	
	† Is life threatening; or places the subject, in the view of the investigator, at immediate risk of death from the event as it occurred (Note: This does not include an adverse event that, had it occurred in a more severe form, might have caused death.); or	
	† Results in a persistent or significant disability/incapacity (substantial disruption of one's ability to conduct normal life functions); or	
	† Results in or prolongs an existing inpatient hospitalization (hospitalization is defined as an inpatient admission, regardless of length of stay, even if the hospitalization is a precautionary measure for continued observation. (Note: Hospitalization for an elective procedure to treat a pre-existing condition that has not worsened is not a serious adverse event. A pre-existing condition is a clinical condition that is diagnosed prior to the use of a Merck product and is documented in the patient's medical history.); or	
	† Is a congenital anomaly/birth defect (in offspring of subject taking the product regardless of time to diagnosis); or	
	Is a new cancer; (that is not a condition of the study) (although not serious per ICH definition, is reportable to the Sponsor within 2 working days to meet certain local requirements); or	
	Is an overdose (whether accidental or intentional). Any adverse event associated with an overdose is considered a serious adverse event for collection purposes. An overdose that is not associated with an adverse event is considered a non-serious event of clinical interest and must be reported within 24 hours to the Sponsor and to Merck within 2 working days...	
	Other important medical events that may not result in death, not be life threatening, or not require hospitalization may be considered a serious adverse event when, based upon appropriate medical judgment, the event may jeopardize the subject and may require medical or surgical intervention to prevent one of the outcomes listed previously (designated above by a †).	
Duration	Record the start and stop dates of the adverse event. If less than 1 day, indicate the appropriate length of time and units	
Action taken	Did the adverse event cause the Merck product to be discontinued?	
Relationship to Merck Product	Did Merck product cause the adverse event? The determination of the likelihood that Merck product caused the adverse event will be provided by an investigator who is a qualified physician. The investigator's signed/dated initials on the source document or worksheet that supports the causality noted on the AE form, ensures that a medically qualified assessment of causality was done. This initial document must be retained for the required regulatory time frame. The criteria below are intended as reference guidelines to assist the investigator in assessing the likelihood between the test drug and the adverse event based upon the available information.	
	The following components are to be used to assess the relationship between Merck product and the AE; the greater the correlation with the components and their respective elements (in number and/or intensity), the more likely Merck product caused the adverse event (AE):	
Exposure	Is there evidence that the subject was actually exposed to Merck product such as: reliable history, acceptable compliance assessment (pill count, diary, etc.), expected pharmacologic effect, or measurement of drug/metabolite in bodily specimen?	
Time Course	Did the AE follow in a reasonable temporal sequence from administration of Merck product?	
Likely Cause	Is the time of onset of the AE compatible with a drug-induced effect (applies to trials with investigational medicinal product)? Is the AE not reasonably explained by another etiology such as underlying disease, other drug(s)/vaccine(s), or other host or environmental factors	

Relationship to Merck product (continued)	The following components are to be used to assess the relationship between the test drug and the AE: (continued)
Dechallenge	Was Merck product discontinued or dose/exposure/frequency reduced? If yes, did the AE resolve or improve? If yes, this is a positive dechallenge. If no, this is a negative dechallenge. (Note: This criterion is not applicable if: (1) the AE resulted in death or permanent disability; (2) the AE resolved/improved despite continuation of the Merck product; or (3) the trial is a single-dose drug trial); or (4) Merck product(s) is/are only used one time.)
Rechallenge	Was the subject re-exposed to Merck product in this study? If yes, did the AE recur or worsen? If yes, this is a positive rechallenge. If no, this is a negative rechallenge. (Note: This criterion is not applicable if: (1) the initial AE resulted in death or permanent disability, or (2) the trial is a single-dose drug trial); or (3) Merck product(s) is/are used only one time). NOTE: IF A RECHALLENGE IS PLANNED FOR AN ADVERSE EVENT WHICH WAS SERIOUS AND WHICH MAY HAVE BEEN CAUSED BY MERCK PRODUCT, OR IF REEXPOSURE TO MERCK PRODUCT POSES ADDITIONAL POTENTIAL SIGNIFICANT RISK TO THE SUBJECT, THEN THE RECHALLENGE MUST BE APPROVED IN ADVANCE BY THE U.S. CLINICAL MONITOR AS PER DOSE MODIFICATION GUIDELINES IN THE PROTOCOL.
Consistency with Trial Treatment Profile	Is the clinical/pathological presentation of the AE consistent with previous knowledge regarding the Merck product or drug class pharmacology or toxicology?
The assessment of relationship will be reported on the case report forms/worksheets by an investigator who is a qualified physician according to his/her best clinical judgment, including consideration of the above elements.	
Record one of the following Yes, there is a reasonable possibility of Merck product relationship.	Use the following scale of criteria as guidance (not all criteria must be present to be indicative of a Merck product relationship). There is evidence of exposure to Merck product. The temporal sequence of the AE onset relative to the administration of Merck product is reasonable. The AE is more likely explained by Merck product than by another cause.
No, there is not a reasonable possibility Merck product relationship	Subject did not receive Merck product OR temporal sequence of the AE onset relative to administration of Merck product is not reasonable OR there is another obvious cause of the AE. (Also entered for a subject with overdose without an associated AE.)

